Clinical Significance: This study will demonstrate the supplemental motor relearning value of virtual reality/video games to CCFES therapy, (2) identify patients most likely to respond to both therapies, and (3) determine whether adding HTVG to CCFES simply enhances cortical activation underlying CCFES or engages additional cortical areas to improve response across broader ranges of severity and chronicity. This study is an important step toward the development and dissemination of new

treatments that may be applicable and effective across a wide range of patients who have lost hand function after stroke.

Specific Aims

AIM 1: Determine the effect of integrating Hand Therapy Video Games (HTVG) with Contralaterally Controlled Functional Electrical Stimulation (CCFES) on upper extremity motor outcomes

Hypothesis 1: Stroke patients treated with CCFES+HTVG will have greater and faster improvements in hand dexterity, upper limb impairment, and activity limitation than those treated with CCFES alone

AIM 2: Evaluate the effect of baseline impairment and time post-stroke on treatment response

Hypothesis 2: Compared to CCFES, CCFES+HTVG will benefit patients with greater baseline impairment and time elapsed post-stroke.

AIM 3: Explore the effects of CCFES+HTVG vs. CCFES on cortical activation during a hand task

Hypothesis 3: Compared to CCFES, CCFES+HTVG will exhibit greater re-mapping in the brain, demonstrated as greater lateralization of activity, greater recruitment of learning- based networks in ipsilesional and contralesional regions, and increased intensity of cortical activity.

Methods and Procedures

General Study Design

A single-blinded randomized controlled trial will be carried out to assess the effects of 12 weeks of CCFES+HTVG compared to CCFES. Dexterity, upper limb impairment, and activity limitation will be assessed at 0 (baseline), 3, 6, 9, 12 (end of treatment), 24, and 36 wks. Cortical activation (measured with fMRI) will be optionally assessed at 0 and 12 wks. The treatment dose will be the same for both groups: 10 sessions per week (7.5 hrs) of self-administered treatment at home plus 2 sessions per week (3 hrs) of group-specific occupational therapy in the lab.

Device

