Lab sessions will last ~1.5 hrs. During the first 20 minutes, the CCFES group will do the repetitive CCFES-mediated hand opening exercise, with the therapist reinforcing instructions to open both hands at the same time in response to the cues. The CCFES+HTVG group will play several minutes of each of the video games they were assigned to do at home, while the therapist adjusts the difficulty levels of the games and/or introduces and teaches a new game. Then, for both groups, for 60 minutes the therapist will instruct and encourage subjects to perform functional tasks with the paretic arm and hand, using CCFES to assist hand opening during task practice. Tasks will involve hand opening and closing to pick up, manipulate, and release objects commonly used in daily life. Task difficulty will progress from easy-to-acquire-and-manipulate to tasks requiring wider hand opening, greater skill, graded hand opening (controlled release), and coordination of hand function with proximal upper limb movement.

Data Collection

Baseline Variables

A clinical coordinator will collect baseline characteristics from the participants' electronic medical record(s) and by interview. Data collected will include demographic (e.g., sex, age, race, pre-morbid hand dominance), stroke-related (e.g., time post-stroke, hemorrhagic or ischemic, cortical or subcortical, right or left, Stroke Impact Scale score), and neurologic data (e.g., side of hemiparesis, cognition, neglect, visual deficits, aphasia), as well as co-morbidities, medications, and cognitive function (Montreal Cognitive Assessment). The balance of these variables between the two groups and their effect on the outcomes will be evaluated.

Adherence

Adherence to the home regimen will be monitored with electronic data logging and participant diaries. The stimulator logs the number of cued hand opening exercise periods completed (CCFES group) and the number of CCFES-mediated hand opening/closing repetitions (both groups). The HTVG system logs game setup/difficulty settings, game performance data (e.g., scores), and number of paretic hand opening/closing repetitions. Participants will also be given a paper diary to log completion of sessions. The diaries will be reconciled with electronic data logs at every lab session, in the presence of the participant to encourage adherence.

Concomitant Therapies

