We will enroll only patients who are no longer receiving rehabilitation therapies to the upper limbs. The use of electrical stimulation or other experimental rehabilitation techniques involving the hemiparetic upper limb, changes in spasticity medications, botulinum toxin injections to upper limb muscles, use of an arm sling, and use of a resting hand splint will be discouraged unless it is deemed medically necessary. To account for the potential confounding effect of such concomitant therapies, all concomitant therapies will be documented and any group imbalance will be accounted for in the statistical analysis.

Upper Limb Motor Assessments

All subjects will undergo assessments of hand dexterity (BBT), upper limb impairment (UEFM, Maximum Voluntary Finger and Elbow Extension and Tracking), activity limitation (AMAT) by a blinded assessor at 0 (baseline), 3, 6, 9, 12 (end of treatment), 24, and 36 wks. All assessments will be done with no electrical stimulation. Subjects will refrain from using their stimulators for 24 hours prior to their 3, 6, 9, and 12 week assessments in order to avoid any transient carry-over effect or muscle fatigue.

Box and Blocks Test (primary)

The BBT is a measure of gross manual dexterity, which requires the subject to pick up one block at a time, move it over a partition, and release it in a target area as many times as possible in a 60-sec period.

Upper Extremity Fugl-Meyer Assessment

The UEFM is a measure of post-stroke upper limb motor impairment. The assessor requests the subject to attempt specific volitional movement of the upper limb (shoulder, elbow, forearm, wrist, and hand), and rates their ability to perform each movement using a 3-point ordinal scale (0, cannot perform; 1, perform partially; and 2, perform fully). The maximum score is 66.

Arm Motor Abilities Test

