- Electrical stimulation should not be used by patients with implanted electronic devices (cardiac demand pacemakers etc.) unless under specialized medical supervision.
- Do not participate in this study if you have a history of potentially fatal cardiac arrhythmias.
- Electrical stimulation should not be used by people who have poorly controlled epilepsy.
- The stimulator has been programmed specifically for the intended user only. Do not let others use the stimulator.

Statistical Analysis Plan

We hypothesize that the CCFES+HTVG group will have greater post-treatment gains than the CCFES group on upper extremity motor outcomes. Exploratory looks at the data will be done before fitting our models. The adaptive randomization should force relatively good balance of potential confounding variables (e.g., fMRI eligible, severity of impairment, time post-stroke), but imbalances in treatment adherence or any other baseline covariate (e.g., lesion location, etc.) or adherence may still require their inclusion as covariates. Each measure will be modeled using a linear mixed effects approach which is well-suited for handling correlated repeated measurements, unbalanced data, and missing data and dropouts in longitudinal studies, while permitting us to control for potential confounders.¹ Least square (LS) means will be calculated using model estimates and adjusted for missing values for each group at each time point. This approach allows comparisons and estimates of treatment group effects at any time point, and also allows comparisons and estimates across time points within groups to evaluate the persistence or decay of the treatment effect. Secondarily, we hypothesized that participants who were less than 2 years after stroke or had moderate hand impairment at baseline would improve more than participants who were more than 2 years after stroke or had severe hand impairment at baseline. A mixed effects modeling analysis will be used similar to the primary analysis to evaluate the effects of time post-stroke and impairment severity. For fMRI data, differences from baseline to EOT in beta coefficient maps for each region of interest will be evaluated with paired t-tests and cluster threshold set to >100 voxels. Between-group comparisons will be made with independent t-tests.

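### Exploratory looks precede model fitting and observed arm imbalances, adherence included, decide the covariates; with no stated masking or model lock, the error rate of the primary Box and Blocks comparison cannot be verified

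*Combined protocol and SAP*

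**What the plan says.** All references are to the combined protocol and SAP.

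- **Order of work (Statistical Analysis Plan).** "Exploratory looks at the data will be done before fitting our models". The section does not say what is examined, by whom, or whether arm is visible.
- **Model (same section).** "Each measure will be modeled using a linear mixed effects approach". Fixed effects, coding of time and covariance structure are not given.
- **Covariates (same section).** The adaptive randomization should balance the main confounders, but "imbalances in treatment adherence or any other baseline covariate (e.g., lesion location, etc.) or adherence may still require their inclusion as covariates". There is no list and no threshold.
- **Time point (same section).** "This approach allows comparisons and estimates of treatment group effects at any time point". Assessments are "at 0 (baseline), 3, 6, 9, 12 (end of treatment), 24, and 36 wks" (Upper Limb Motor Assessments), which gives six post-baseline visits. The BBT is labelled primary, but no visit is.
- **Baseline data (Data Collection, Baseline Variables).** "The balance of these variables between the two groups and their effect on the outcomes will be evaluated".
- **Concomitant Therapies.** "all concomitant therapies will be documented and any group imbalance will be accounted for in the statistical analysis".
- **Masking (General Study Design).** "A single-blinded randomized controlled trial will be carried out". Elsewhere blinding is described only for the outcome assessor. Nothing is said about the analyst.

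No significance level, sidedness or model lock appears anywhere.

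**The concern.** The plan looks first and settles the model afterwards, and what it looks for includes differences between arms. An imbalance cannot be found without splitting the data by group, so arm enters the choice of covariates. The Baseline Variables section adds the relation of the same variables to the outcomes. With no lock between these steps, a later reader could not tell a planned model from a selected one.

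Adherence is a separate problem. It is measured after randomization and may itself be affected by the arm, since one arm's home sessions are video games and the other's are cued exercise. Adjusting the primary comparison for it changes what is being estimated.

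At stake is the primary BBT comparison, which rests on at most 52 people. At that size, a change of covariates can move a p-value across a threshold.

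**Working it through.** **Inputs from the documents.** Up to 52 participants in two arms (Methodology); six post-baseline visits; covariates open; adherence a named candidate. There is no stated error rate or power to reproduce.

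**Inputs assumed.** Two-sided 5%; 26 per arm (the allocation ratio is not stated); the number and strength of the candidate covariates.

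**Step 1. Simulated false-positive rates with no true arm effect.** Set A: least squares on one outcome without the baseline score, 4 or 8 candidates, correlation 0.2 to 0.3 with outcome, 1,500 trials per setting. Set B: baseline-adjusted analysis, 3 or 5 candidates with coefficients 0.1 to 0.3, six visits with residual within-person correlation 0.8, 2,000 to 3,000 trials per setting (the first 1,000 for the last row).

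| How the model is chosen | Set A | Set B |
|---|---|---|
| Fixed in advance | 4.3–5.1% | 4.1–5.8% |
| Covariates by pooled association with outcome, arm not used | 4.2–5.3% | 4.1–5.5% |
| Covariates added when imbalanced between arms (A: p<0.10; B: p<0.2) | 2.8–4.0% | 3.3–5.5% |
| Covariate set with the smallest arm p-value | 9.2–20.8% | 6.0–17.0% |
| Visit with the smallest arm p-value | not run | 11.5–13.5% |
| Covariate set and visit with the smallest arm p-value | not run | 19.7–38% |

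In Set A the smallest-p rule ran over all models with no, one or two covariates: 9% (4 candidates, r = 0.2), 15% (8, r = 0.2) and 21% (8, r = 0.3). At r = 0.1 it gives 7% (4) and 10% (8). A further run of the imbalance rule gave 2 to 4%.

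The simulation standard error at a true 5% is √(0.05 × 0.95 / 1,500) = 0.56 points in Set A and √(0.05 × 0.95 / 3,000) = 0.40 points at the larger size in Set B. The first two rows are 5% to within a little over two standard errors.

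If the six visits were independent, choosing the best would give 1 − 0.95⁶ = 26.5%. The correlation between visits brings this down to 11.5 to 13.5%.

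**Step 2. Baseline imbalance.** The third row is the rule that the plan actually describes for baseline variables. It does not inflate the error. It leaves it at or somewhat below nominal, about 2 to 5%.

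**Step 3. Adherence.** Let b be the within-arm slope of outcome on adherence and δ the arm difference in mean adherence, both in SD units. If arm has no effect on outcome and adherence only marks something prognostic, the adjusted arm estimate is centred on −bδ instead of 0. With b = 0.2 to 0.3 (the range used above) and δ = 0.5 (assumed):

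- bias = 0.2 × 0.5 = 0.10 to 0.3 × 0.5 = 0.15 outcome SD;
- standard error ≈ √(2/26) = 0.277, so bias/SE = 0.36 to 0.54;
- rejection rate = Φ(−1.96 + 0.36) + Φ(−1.96 − 0.36) = 5.5% + 1.0% = 6.5%, up to Φ(−1.96 + 0.54) + Φ(−1.96 − 0.54) = 7.8% + 0.6% = 8.4%.

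At δ = 0 the rate returns to 5%. A simulation with adherence as the imbalanced covariate gave 6 to 8%, in line with this. If instead the games work partly by raising adherence, the adjustment removes part of the effect that the trial is meant to estimate.

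**Step 4. What drives inflation.** Among the rules for baseline covariates and visits, only those that use the arm result on the outcome exceed 5% materially. Choosing on pooled data does not.

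**The case against.** A reader might infer that the looks are done unmasked and that a nominal 5% error rate is therefore lost. The documents do not support this. They are silent on masking, and they state no significance level that could be lost. Exploratory looks before a mixed model can mean distributions, outliers and missing data, none of which requires the arm contrast. The only stated trigger for adding a covariate is imbalance, which for baseline variables does not inflate the error. The 9 to 21% comes from picking the smallest p-value, a rule that the plan proposes nowhere, under correlations and candidate numbers that the documents do not supply. Conditioning on baseline BBT would plausibly weaken those correlations.

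There is also real protection. The model family is fixed for each measure, the assessor is blinded, and minimization on four factors reduces imbalance on those factors. The Baseline Variables sentence does not say that its checks come before the primary model.

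All of this stands as a limit on size. It does not close the gap. Detecting imbalance needs data split by arm, no lock separates that step from the outcome analysis, and adherence is expressly a candidate covariate. The blinded assessor protects measurement, not model choice.

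**Conclusion.** The concern holds as a failure to secure the primary analysis, not as a demonstrated inflation. Because observed imbalances decide the covariates, and neither masking nor a model lock is stated, the error rate of the primary BBT comparison cannot be verified.

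The stated rule is mildly conservative for baseline covariates. For adherence it can bias the arm estimate, by bδ, whatever the analyst's intentions. The 9 to 21% range marks what the plan leaves possible, not what it prescribes. The open choice of visit is of similar weight to the choice of covariates and should be closed with it.

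The figures rest on two-sided 5%, 26 per arm, assumed correlations, and single-visit linear models standing in for the mixed model. Their ordering is more secure than their size.

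**What to change.** In the Statistical Analysis Plan, replace the sentence on exploratory looks and the one on imbalances with:

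> Exploratory looks before model lock will use pooled data or scrambled arm codes, with arm-revealing device and game logs withheld. The primary BBT contrast and time point, baseline covariates (baseline score and the four minimization factors), coding of time and covariance structure will be fixed in a dated SAP before arm codes are joined to outcomes. Models prompted by observed imbalances, and any model adjusting for adherence, are sensitivity analyses only.

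Three notes on carrying it out:

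- Scrambled should mean permuted across participants. Relabelling the arms A and B leaves the size of the contrast and its two-sided p-value in view.
- The logs matter because, under Adherence, cued exercise periods are recorded for the CCFES group and game settings and scores come from the HTVG system. Either shows the arm even when the code is hidden.
- The same dated SAP should state the significance level and sidedness, and the Concomitant Therapies text should be aligned, since therapies started during the trial are also post-randomization.

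The cost is SAP wording and some data handling. No visit, procedure or sample size changes. The downside is that a model change after lock, even a sensible one, can only be reported as a sensitivity analysis.

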Stimulation is delivered through standard self-adhering pre-gelled 2"x2" square and 1.25" round electrodes (e.g., PALS®, Axelgaard Manufacturing, Fallbrook, CA). The analog input source for the stimulator is an assembly of three passive bend sensors 1/4" wide by 4 1/2 " long (Spectra Symbol, Salt

Lake City, UT) which are either attached by Velcro or inserted through slits cut into the top of the index, middle, and ring fingers of an athletic glove.³ The sensors act as variable resistors. When the fingers open and close, the electrical impedance of each sensors changes; these impedance changes are supplied as the analog input to the stimulator. The stimulator is programmed to produce current pulses with pulse widths (intensities) that are proportional to input from the glove worn on the nonparetic hand.

The CCFES+HTVG system uses a bend sensor that is worn on a finger of the paretic hand to detect opening and closing. The sensor is attached to a fingerless “glove” and plugs into an analog-to-digital converter module, which in turn plugs into a USB port on a 17-inch touchscreen laptop computer. The computer is an all-in-one unit that requires no other components besides the monitor’s touchscreen (no keyboard or mouse) to select and play the games. The computer is configured so that it can only be used for the game play prescribed to the participant and requires a USB key from the investigators to run.

Randomization

Subjects will be assigned to a treatment group using an adaptive randomization algorithm⁵ to minimize group imbalances on 4 key patient characteristics: (1) time post-stroke (< 2 yrs vs. \geq 2 yrs), (2) baseline motor status (moderate vs. severe), (3) paretic side (dominant vs. non-dominant),⁶ and (4) fMRI eligibility (yes vs. no). Patients with $\geq 10^\circ$ active wrist extension, 10° active thumb abduction/extension, and 10° active extension in at least two additional digits will be considered to have “moderate” impairment, and patients with less movement than that who meet all the other motor criteria (see Section 30) will be considered to have “severe” impairment.⁷

Device Set Up

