For the CCFES group, during each of three 15-min periods, audio cues issued from the stimulator will prompt the subject to attempt to fully open both hands for several seconds, then relax both hands for several seconds, and repeat the cycle. Stimulation will open the paretic hand when the subject opens the contralateral unimpaired hand. The subjects will be instructed to attempt to exert effort to open the paretic hand at the same time they open their non-paretic hand. As in our previous studies, the cue durations will be adjusted every 2 weeks, starting at 6 sec open/14 sec relax (30% duty cycle),

then changing to 8 sec open/12 sec relax (40% duty cycle), and finally 10 sec/10 sec (50% duty cycle). These duty cycles are within the 20% to 50% range of duty cycles used in other NMES studies.⁸⁻¹² The purpose of the graded duty cycle is to prevent fatigue early in the intervention and to progressively build greater strength with longer duration muscle contractions.¹⁰ A 3-minute rest will follow each 15-minute period.

For the CCFES+HTVG group, during each of three 15-minute periods, the subject will play one of the 4 previously described games, switching to another game every 15 minutes with a 3-minute break between games. The subjects will use the CCFES system to assist hand opening and will be instructed to exert effort to open the paretic hand at the same time they open their non-paretic hand while playing the games. Because games will be introduced and taught one at a time over the first 4 weeks, during the first two weeks of treatment, the subject will have only learned to play one or two games and therefore will repeat the same game over multiple 15-min periods within a single session. More games will be added (unlocked) as the subject learns them in the lab. The therapist will unlock games and set the difficulty settings for each game at the lab sessions. These settings will be stored on a USB key, which the subject must plug into the home computer in order to play the games at home.

Therapist-Administered Lab Sessions

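### The SAP lets adherence, and the protocol requires concomitant therapies, to enter the treatment comparison on observed imbalance, although both arise after randomisation; it also leaves the primary model's baseline terms open

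*Combined protocol and SAP*

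**What the plan says.** **Adherence.** The Statistical Analysis Plan expects adaptive randomisation to balance potential confounders, "but imbalances in treatment adherence or any other baseline covariate (e.g., lesion location, etc.) or adherence may still require their inclusion as covariates". The sentence names adherence twice and classes it with baseline covariates. The Adherence section under Data Collection shows that it is collected during the home regimen, from electronic logs and a paper diary of sessions that is reconciled with the logs at each lab visit. On the logs it says "The stimulator logs the number of cued hand opening exercise periods completed (CCFES group) and the number of CCFES-mediated hand opening/closing repetitions (both groups".

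**Concomitant therapies.** The protocol section of that name says "all concomitant therapies will be documented and any group imbalance will be accounted for in the statistical analysis".

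**Primary model.** The SAP specifies a linear mixed effects approach, "while permitting us to control for potential confounders", and then "Least square (LS) means will be calculated using model estimates and adjusted for missing values for each group at each time point". It gives no list of fixed effects and does not define imbalance. It plans exploratory looks before models are fitted. The Randomization section uses an adaptive algorithm "to minimize group imbalances on 4 key patient characteristics": time post-stroke, motor status, paretic side and fMRI eligibility. The SAP cites three of these as examples of variables expected to balance. It models time post-stroke and severity in a secondary analysis.

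**The concern.** Aim 1 asks what adding HTVG to CCFES does to motor outcome. Games may work partly by changing how much patients practise. If so, conditioning on practice removes part of the effect the trial is meant to measure. If practice has no causal role, a trait such as motivation that drives both adherence and recovery still biases the adjusted contrast once the arms differ in adherence. The same logic applies to concomitant therapies begun or changed after randomisation.

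The adjustment is brought in by an observed difference between arms, which is the situation in which it changes the estimate. With no definition of imbalance and no fixed model, the decision would be made after looking at the data.

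The open baseline terms matter less. They affect precision and the freedom to choose a model, not bias.

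**Working it through.** **Nothing to reproduce.** The plan gives no effect size, SD, correlation, alpha, allocation ratio or adherence spread. It gives only a maximum of 52 patients. Everything below assumes 26 per arm, two-sided 5% tests and outcomes in within-arm SD units.

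**Step 1: timing.** Time post-stroke, severity, paretic side, fMRI eligibility and lesion location are fixed before assignment. Adherence to the 12-week home regimen and therapies used during the study are not. The SAP sentence applies one imbalance rule to both kinds of variable.

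**Step 2: expected value of the adherence-adjusted contrast.** Let δ be the adherence difference (HTVG minus CCFES, in SD), τ the total treatment effect, and λ the within-arm slope of gain on adherence. Then

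adjusted contrast = τ − λδ.

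Let an unmeasured trait U load 0.4 on adherence and 0.4 on gain.
- If adherence also has a causal effect of 0.3, λ = 0.3 + 0.4 × 0.4 = 0.46.
- If adherence has no causal effect, λ = 0.4 × 0.4 = 0.16.

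With τ = 0.8:

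| δ | λ = 0.46 | λ = 0.16 |
|---|---|---|
| 0 | 0.80 | 0.80 |
| +0.3 | 0.8 − 0.138 = 0.66 | 0.8 − 0.048 = 0.75 |
| +0.5 | 0.8 − 0.230 = 0.57 | 0.8 − 0.080 = 0.72 |
| +0.8 | 0.8 − 0.368 = 0.43 | 0.8 − 0.128 = 0.67 |
| −0.3 / −0.5 / −0.8 | 0.94 / 1.03 / 1.17 | 0.85 / 0.88 / 0.93 |

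Simulation agrees (0.66, 0.57 and 0.43 to 0.44 for positive δ at λ = 0.46). Adjusting only when the adherence difference has p<0.05 gives about 0.74, 0.65 and 0.47 at λ = 0.46.

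**Step 3: power at τ = 0.8.** Unadjusted power is about 81%. For δ = 0.3/0.5/0.8:
- λ = 0.46, always adjusted: about 73/59/35%.
- λ = 0.16, adjusted only if p<0.05: about 77/73/61%.

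**Step 4: rejection when the total effect is zero**, for δ = 0.3/0.5/0.8:

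| Rule | λ = 0.46 | λ = 0.16 |
|---|---|---|
| Always adjust | about 8–9 / 14 / 27% | about 5 to 7% |
| Adjust only if p<0.05 | about 5–6 / 9 / 23% | about 4 to 7% |

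The error goes against HTVG when its adherence is higher and in its favour when lower. At λ = 0.46 a zero total effect implies a direct effect of −0.3δ, so part of that rejection reflects a different target rather than pure error. At λ = 0.16 it is confounding alone.

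**Step 5: baseline terms (efficiency only).** Suppose week 0 is an unconstrained response and data are complete. The week-12 contrast is then a change score with variance factor 2(1 − ρ), against 1 − ρ² with baseline adjustment. At ρ = 0.6 these are 0.80 and 0.64. For a 0.5 SD effect, power is 51/80/98% against 60/84/98% at ρ = 0.6/0.8/0.9.

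For the minimisation factors, with baseline in both models and ρ = 0.6:

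| Baseline-adjusted variance explained | Power without | Power with | Type I error without |
|---|---|---|---|
| 5% | 58% | 58% | 5.0% |
| 10% | 61% | 64% | 4.3% |
| 20% | 58% | 67% | 3.2% |
| 30% | 60% | 74% | 2.8% |

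If the factors only shift the level of the score, the gain is at most about 4 points.

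**The case against.** **The wording is permissive.** The SAP says imbalance may require inclusion, and the Concomitant Therapies section does not say which analysis will do the accounting. Both could be honoured by sensitivity analyses. This stands as far as it goes: the plan does not mandate an adjusted primary estimate. But the SAP sentence sits in the description of the outcome models, and nothing restricts it.

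**The arms are built for equal dose.** The Abstract and General Study Design say so, and interest in the effect at equal delivered dose is reasonable. That is a different question from the total effect, and regression on observed adherence need not answer it without bias.

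**Concomitant-therapy imbalance may be small.** Only patients no longer receiving upper-limb rehabilitation are enrolled, and other therapies are discouraged. No size is claimed for this part.

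**Stronger readings the documents do not support.**
- A reader might infer that an adherence imbalance is built in, because the repetition count is the log named for both groups. In the CCFES home sessions each cue setting makes a 20-second cycle (6+14, 8+12, 10+10), or 3 per minute, while no cue cycle is given for game play. But the plan never selects repetitions as its adherence measure and gives no game rate. The Device section says the stimulator stores usage statistics, and session diaries are kept in both arms. Only a caution remains.
- A reader might infer a type I error near a quarter. That needs the higher slope and the largest imbalance; at the lower slope it stays near nominal.
- A reader might infer that baseline is ignored, or that omitting the minimisation factors biases the result. The SAP's hypothesis concerns gains, and week 0 is a scheduled assessment, which suggests change from baseline. Omitting balanced factors makes the test conservative.

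**Conclusion.** The concern holds for the covariate rule. The plan treats a post-randomisation variable as a baseline one and allows an observed difference to bring it into the treatment comparison. It commits to something similar for concomitant therapies. Where the arms differ, the adjusted contrast is not the total effect of adding HTVG, and the bias can run either way.

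At a 0.5 SD adherence difference, a true 0.8 SD effect moves by 0.08 to 0.23 SD across the two slopes considered. This rests wholly on assumed slopes, adherence differences and equal allocation. With no adherence difference there is no bias and the test keeps its level. The documents do not show that such a difference will occur.

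The uncommitted minimisation factors and baseline term are a secondary matter of power and prespecification. The plan should be changed on both counts, chiefly on the first.

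**What to change.** 1. State that adherence and concomitant therapies do not enter the primary comparison. Report models that adjust for them only as labelled sensitivity analyses. Define adherence there by a measure with the same meaning in both arms, such as completed sessions from the reconciled diary. Treat logged repetitions with caution, because cues set the pace in the CCFES arm only.
2. List the primary Box and Blocks model in advance: arm, visit, arm by visit, baseline score (as covariate by visit, or week 0 as a response with baseline means constrained equal) and all four minimisation factors, always included. If week 0 is a response, the factors enter by visit.
3. Name any further baseline covariate, such as lesion location, in advance. Exploratory looks may stay but should not choose covariates.

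**Cost.** SAP wording and a few degrees of freedom; the variables are already collected. A simulated repeated-measures model (six post-baseline visits, 15% dropout) compared week-12 power with baseline only, plus factor main effects, and plus factor by visit. It was 55.8/54.8/54.5% when the factors predict nothing, a loss of about one point, and 60.3/64.7/65.0% when they explain 20%.
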